This study will investigate the 'diagnostic accuracy' of diarrhoea self-report for enteric infection by evaluating against the sampling of stool for analysis of faecal pathogens and biomarkers of infection. Not only does this provide a means to estimate the association between infection and reported diarrhoea, but it also allows for measurement of asymptomatic infection – which is still a target of WASH interventions. This study will randomise participants into one of two diarrhoea measurement arms for surveys: a basic survey for infant diarrhoea (similar to DHS) and an enhanced survey for infant diarrhoea (using tools such as the Bristol stool scale); and subsequently randomly selecting a subgroup from each arm to undergo faecal stool testing of infants. The primary outcomes will be the positive and negative predictive values of self-reported diarrhoea for enteric infection. As a secondary outcome we will examine the types of pathogen present. We would conduct a survey at baseline in February/March, a time with low diarrhoeal disease incidence; and June/July, a time with high diarrhoeal disease incidence - to account for seasonality, and to measure variation in respondent fatigue for the various methods. This research will take place in the Cox's Bazar refugee camp, which may also allow for analysis of the burden of carriage of disease which is not endemic to Bangladesh.

Background

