Within each arm at each time point, 20 households reporting diarrhoea, and 20 not reporting diarrhoea, will be selected to have the oldest infant under 5 undergo stool testing - a total of 80 households at each time point, 160 in total. The first 20 households reporting diarrhoea and not reporting diarrhoea in each arm will be selected and asked if they are willing to provide stool samples. A WhatsApp group will be created for the research assistants to determine when 20 consenting households have been reached in each arm. The consenting households will be given a stool collection container once the survey has been administered, which will be collected the following day. All stool containers will be labelled with a barcode which will be scanned by the research assistant using a tablet, to link the stools sample with the survey. Stool will be collected by the carer, and tested for the presence of predetermined organisms which are endemic to the Rohingya population, along with a small number of select pathogens that are not endemic (Table 1); and for the presence of biological markers of infection: calprotectin and lactoferrin. This will be done through the use of polymerase chain reaction analysis (PCR) at the laboratory at the ICDDR,B in Dhaka, Bangladesh. Stool will also be tested for blood using a faecal hemooccult test.

Туре	Species	Carriage period (adults)	Carriage period (children)
Bacteria	Shiga toxin-producing Escherichia	17-18 days (1)	35-69 days (2)
	Enteropathogenic Escherichia coli	ND	20—36 days (2)
	Enterotoxigenic Escherichia Coli	ND	<5 days (2)
	Enteroinvasive Escherichia Coli	ND	ND
	Enterohemorrhagic Escherichia Coli	ND	2-62 days (2)
	Salmonella typhi	12-25 days (3)	Varies (2)
	Salmonella paratyphi	28-55 days (4)	~30 days (2)
	Campylobacter	14-21 days (5)	Up to 6 weeks (5)
	Shigella	~28 days (6)	1-10 days (6)
	Cholera	~2 days (7)	~4 days (7)
	C. difficile	6-57 days (8)	6-57 days (8)
	C. perfringens	ND	ND
	Acinetobacter	7-11 days (9)	ND
Protozoa	Entamoeba histolytica	ND	ND
	Cryptosporidium	~8 days (10)	~8 days (10)
	Cyclospora	5-13 days (11)	22-23 days (11)
	Giardia	2-6 weeks (12)	~6 months (13)
Helminth	Ancylostoma duodenale	1-2 years (14)	ND
	Ascaris lumbricoides	Years (15)	Years (15)
Viruses	Rota-virus	Up to 35 days (16)	4-57 days (2)
	Hepatitis A	~21 days (17)	Up to 21 days (12)
	Hepatitis E	3-4 weeks (18)	ND
	Norovirus	ND	8-60 days (19)
	Human Caliciviruses	~14 days (20)	~12 days (20)
	Adenovirus	ND	8-23 days (20)

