	Astrovirus	ND	1-10 days (20)
Fungi	Enterocytozoon	18-38 days (21)	9-40 days (22)

Informed consent

All respondents will be consented in the Rohingya language and given a demographic and behaviour survey at the first time point. All questionnaires and surveys will be translated into Rohingya and back translated into English, with all data collection will be completed by Rohingya research assistants.

Data analysis

Data will be analysed using Stata version 15. The following analyses will be conducted

- Incidence rate ratios and associated 95% confidence intervals comparing diarrhoea and dysentery incidence between:
 - o Enhanced and basic surveys
 - o Survey method and stool analysis method
- Positive predictive value and associated 95% confidence interval of reported diarrhoea for the presence of enteric pathogens
- The association between diarrhoea presence and other potential markers of enteric infection such as MUAC and water-related diseases, measured for example by Jaccard's index
- A logistic regression of diarrhoea prevalence on demographic and health variables to examine association.

All missing data will be reported and assumed to be missing at random. The sample sizes proposed here would give us power to estimate the self-reported diarrhoea rate in each arm to a 95% confidence interval of approximately ±4 percentage points, assuming a point prevalence of 10%. We would also be able to estimate the positive and negative predictive values to approximately ±7 percentage points assuming values of 90%.

Data Management

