
Has this child had 3 or more loose or watery stools any day in the past 2 weeks?	Yes	No
Has this child had blood in their stool in the past 2 weeks?	Yes	No

If yes to either, did you seek treatment for either of these?	Yes	No	
	lf yes, where?		

Enhanced Survey (50% of respondants)

IDENTIFY OLDEST CHILD UNDER 5												
Mid-Upper Arm Circumference			cm									
*SHOW AMSTERDAM	Consistency	А	В	С	D			_				
CHART*Has the child had any of these stools in the past 2 weeks	Colour	1	2	3	4	5	6					
How long ago?	1		2			3		4	5	6	7	Other:
How many times on the worst day?	1		2			3		4	5	6	7	Other:
How many days did it last?	1		2			3		4	5	6	7	Other:

References

- 1. Vonberg, Ralf P., et al. "Duration of Fecal Shedding of Shiga Toxin–Producing Escherichia Coli O104:H4 in Patients Infected During the 2011 Outbreak in Germany: A Multicenter Study." *Clinical Infectious Diseases*, vol. 56, no. 8, 2013, pp. 1132–1140., doi:10.1093/cid/cis1218.
- 2. ECDC. Systematic Review on the Incubation and Infectiousness/Shedding Period of Communicable Diseases in Children. 2016, Systematic Review on the Incubation and Infectiousness/Shedding Period of Communicable Diseases in Children, ecdc.europa.eu/sites/portal/files/media/en/publications/Publications/systematic-review-incubation-period-shedding-children.pdf.
- 3. Murase, T, et al. "Fecal Excretion of Salmonella Enterica Serovar Typhimurium Following a Food-Borne Outbreak." *JOURNAL OF CLINICAL MICROBIOLOGY*, vol. 38, no. 9, 2000.
- 4. Gunn, John S., et al. "Salmonella Chronic Carriage: Epidemiology, Diagnosis, and Gallbladder Persistence." *Trends in Microbiology*, vol. 22, no. 11, 2014, pp. 648–655., doi:10.1016/j.tim.2014.06.007.
- 5. Janssen, R., et al. "Host-Pathogen Interactions in Campylobacter Infections: the Host Perspective." *Clinical Microbiology Reviews*, vol. 21, no. 3, 2008, pp. 505–518., doi:10.1128/cmr.00055-07.
- 6. South Australia Health. "Shigella Infection Including Symptoms, Treatment and Prevention." SA Health, 2018, www.sahealth.sa.gov.au/wps/wcm/connect/public+content/sa+health+internet/health+topics/health+conditions+prevention+and+treatment/infe ctious+diseases/shigella+infection/shigella+infection+-+including+symptoms+treatment+and+prevention.
- 7. Weil, Ana A., et al. "Bacterial Shedding in Household Contacts of Cholera Patients in Dhaka, Bangladesh." *The American Journal of Tropical Medicine and Hygiene*, vol. 91, no. 4, 2014, pp. 738–742., doi:10.4269/ajtmh.14-0095.

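### Survey versus stool analysis: an incidence rate ratio is not a measure this design can give, and a crude ratio would be driven by the 20:20 stool quota

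*Protocol*

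**What the plan says.** The first item in the protocol's Data analysis list is "Incidence rate ratios and associated 95% confidence intervals comparing diarrhoea and dysentery incidence between" two pairs: the enhanced and basic surveys, and "Survey method and stool analysis method". The second pair is the subject here.

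The inputs to it are described elsewhere in the protocol:

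- **Survey.** The basic form in Appendix 3 asks "Has this child had 3 or more loose or watery stools any day in the past 2 weeks", answered yes or no. The enhanced form uses the same two-week window, and also asks how long ago the episode was and how many days it lasted.
- **Stool.** Under Stool sampling, one specimen per child is "tested for the presence of predetermined organisms which are endemic to the Rohingya population", plus a few other pathogens, two inflammation markers and occult blood. Table 1 lists carriage periods from days to years.
- **Linkage.** The container barcode is scanned "to link the stools sample with the survey", so both results belong to one child.
- **Selection.** "Within each arm at each time point, 20 households reporting diarrhoea, and 20 not reporting diarrhoea, will be selected".

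The Executive Summary names PPV and NPV as the primary outcomes. The Data analysis section itself speaks of point prevalence and diarrhoea prevalence when it describes the same survey outcome.

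**The concern.** An incidence rate needs new events and time at risk. The basic form and the stool test provide neither. The two sides of the ratio also measure different things, since PCR finds organisms whether or not the child has diarrhoea. Of the stool tests, only occult blood bears on dysentery. The results are matched within child, and the reported rate among tested children is fixed by the sampling rule.

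The study's aim is to judge reported diarrhoea rates as a proxy for infection, and this is the listed analysis that sets the two rates against each other. Run literally, it would return a figure that reflects the quota more than the camp.

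**Working it through.** **Inputs.** 400 households, allocated 1:1, so 200 per arm (Sampling; Diarrhoea survey). Reporting rate r = 0.10 and PPV = NPV = 0.90 (Data analysis). Share of reporters among tested children q = 20/40 = 0.5, if the quotas fill (Stool sampling). 160 stool samples in total, 80 from reporters and 80 from non-reporters.

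**Step 1: the plan's own precision.** Half-width = 1.96 × √(p(1 − p)/n).
- Reported rate: 1.96 × √(0.1 × 0.9/200) = 4.2 points, stated as 4.
- Predictive values: 1.96 × √(0.9 × 0.1/80) = 6.6 points, stated as 7. This pools all 80 reporters, or all 80 non-reporters, over arms and rounds.

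Both figures reproduce, and nothing below alters them.

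**Step 2: is either measure an incidence?** The basic item is a two-week period prevalence with no onset date. The stool result is a point prevalence of carriage or infection. The enhanced form would allow onset to be approximated, but in one arm only and not for stool. The survey-versus-stool contrast therefore cannot be an incidence ratio.

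**Step 3: what the quota does.**
- Weighted to the survey: r × PPV + (1 − r)(1 − NPV) = 0.1 × 0.9 + 0.9 × 0.1 = 0.18.
- Crude in the tested sample: q × PPV + (1 − q)(1 − NPV) = 0.5 × 0.9 + 0.5 × 0.1 = 0.50.
- Inflation: 0.50/0.18 = 2.8.
- Stool-to-survey ratio: 0.50/0.50 = 1.0 inside the sample; 0.50/0.10 = 5.0 against the full-survey rate; 0.18/0.10 = 1.8 weighted.

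The same formulas with r = 0.10, PPV = 0.90 and other values of NPV:

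| NPV | Weighted | Crude | Inflation | Ratio inside sample | Ratio against survey | Weighted ratio |
|---|---|---|---|---|---|---|
| 100% | 0.09 | 0.45 | 5.0 | 0.9 | 4.5 | 0.9 |
| 90% | 0.18 | 0.50 | 2.8 | 1.0 | 5.0 | 1.8 |
| 70% | 0.36 | 0.60 | 1.7 | 1.2 | 6.0 | 3.6 |
| 50% | 0.54 | 0.70 | 1.3 | 1.4 | 7.0 | 5.4 |
| 30% | 0.72 | 0.80 | 1.1 | 1.6 | 8.0 | 7.2 |

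At 20% reporting and PPV = NPV = 90%, the weighted value is 0.2 × 0.9 + 0.8 × 0.1 = 0.26 and the inflation 0.50/0.26 = 1.9. The two crude ratios always differ by q/r, which is 5 at 10% reporting.

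**Step 4: pairing.** Take all 160 samples as independent children with PPV = NPV = 90%. Then a = 72 reported and infected, b = 8 reported only, c = 8 infected only. Standard errors of the log ratio inside the sample:
- Paired: √((b + c)/((a + b)(a + c))) = √(16/6400) = 0.050.
- Independent binomial: √(0.5/80 + 0.5/80) = 0.112.
- Ordinary Poisson rate ratio: √(1/80 + 1/80) = 0.158.

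The ordinary interval is 0.158/0.050, about three times too wide on the log scale.

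**The case against.** The strongest reply is that the primary results do not depend on this line. PPV and NPV condition on reported status, which is the variable used for selection, so the quota does not bias them within an arm and round. One minus NPV already gives infection among non-reporters. That stands, and it sets the severity.

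Several stronger readings are tempting, and the documents do not support them:

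- **That the protocol plans an unweighted analysis.** It does not say so. Weighting could sit in an SAP, which was not available. But weighting would not turn these data into incidence, so the named measure is wrong either way.
- **That infection prevalence would be several-fold too high.** That depends on NPV and the reporting rate. The Background allows for possibly high asymptomatic carriage, which would mean a low NPV and little inflation of prevalence. The ratio inside the sample does not benefit: at NPV 50% it reads 1.4 against a weighted 5.4.
- **That the interval would be falsely precise.** An unpaired interval errs on the wide side, and the protocol does not specify one.
- **That enhanced versus basic is equally affected.** Both forms use the same two-week window, so a rate ratio and a prevalence ratio give the same point estimate. A model-based Poisson standard error would be too wide by 1/√(1 − p): about 5% at 10% prevalence and 12% at 20%. That is minor and conservative.
- **That sensitivity would be misreported.** Sensitivity and specificity are not in the analysis list, although the Executive Summary says "This study will investigate the 'diagnostic accuracy' of diarrhoea self-report for enteric infection".

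**Conclusion.** The point holds for the survey-versus-stool comparison. The protocol fixes a measure that its data cannot give, and the crude version of it is a quota artefact: 1.0 or 5.0, depending on the denominator, against 1.8 when weighted, at the protocol's own assumptions. These sizes assume filled quotas, 10% reporting in every arm and round, and tested children who represent their reporting stratum. The 2.8-fold inflation belongs to the 90% predictive values, and the three-fold excess in interval width belongs to the ratio inside the subsample only. Because the comparison is tied to the aim but is not a primary outcome, it should be fixed before analysis and does not put the main results in doubt.

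**What to change.** In Data analysis, replace the incidence rate ratio with a prevalence ratio with robust variance, and drop the word incidence.

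For survey against stool, state that reported diarrhoea is compared with infection prevalence. Weight each tested child by the reporting fraction of its arm and round, using the numbers actually tested. Treat the two results as paired, with robust variance. State the assumption behind the weights: the first 20 consenting households represent their reporting stratum. If sensitivity and specificity are reported, use the same weights. At the plan's values sensitivity is 0.09/0.18 = 50% weighted, against 0.45/0.50 = 90% unweighted.

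The change needs no new data and a few more lines of code. The cost is precision. With strata pooled and r treated as known, the standard error of infection prevalence rises from √(2 × 0.5² × 0.09/80) = 0.024 to √((0.1² + 0.9²) × 0.09/80) = 0.030. On the log scale that is 0.024/0.50 = 0.047 against 0.030/0.18 = 0.17. The weighted ratio of 1.8 would then carry a 95% interval of about 1.3 to 2.5 (1.8 × exp(±1.96 × 0.17)), and somewhat wider once uncertainty in r is included.

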Diarrhoea is one of the two most common causes of death and morbidity in children under five (Kaseebaum, 2016) (Lilford et al, 2017). Upgrades to water and sanitation facilities are a key strategy to deal with this problem, for which proper monitoring and evaluation is needed to determine which interventions are working for a context, and which are not. A primary endpoint for determining the effectiveness of water and sanitation of infections is diarrhoea prevalence, both a primary endpoint in itself, in that diarrhoea is a substantial cause of morbidity and mortality in infants residing in areas with poor access to water and sanitation services; and a proxy marker for enteric infection, which in itself is may be flawed due to possibly high rates of asymptomatic carriage. As we describe, however, there are substantial concerns over the measurement of diarrhoea. We hypothesise that measurement issues may have contributed to the variable and often unexpectedly null results of recent studies, especially cluster trials, of various interventions, and are conducting this study to determine the effect of these biases (Luby et al, 2018) (Null et al, 2018).

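### If any detection on the 27-target panel counts as infection, PPV alone cannot show that self-report is accurate, and the assumed 90% NPV is unsupported

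*Protocol*

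**What the plan says.** The Executive Summary states: "The primary outcomes will be the positive and negative predictive values of self-reported diarrhoea for enteric infection". It frames the study as one of diagnostic accuracy, and adds that the design also lets asymptomatic infection be measured.

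Under Stool sampling, each sample is "tested for the presence of predetermined organisms which are endemic to the Rohingya population"; a few non-endemic pathogens are added to the panel. Samples are also examined "for the presence of biological markers of infection: calprotectin and lactoferrin". Table 1 gives 27 targets: 13 bacteria, 4 protozoa, 2 helminths, 7 viruses and 1 fungus. Twenty reporting and twenty non-reporting households are sampled per arm and time point.

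The Data analysis section lists, as its predictive-value analysis, "Positive predictive value and associated 95% confidence interval of reported diarrhoea for the presence of enteric pathogens". NPV does not appear in that list. The association analysis concerns mid-upper arm circumference and water-related diseases. The rate ratio between survey method and stool analysis compares overall rates, not agreement within children.

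The same section says the study can "estimate the positive and negative predictive values to approximately ±7 percentage points assuming values of 90" per cent. The Background says that diarrhoea as a proxy for infection "may be flawed due to possibly high rates of asymptomatic carriage".

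**The concern.** A predictive value mixes two things: how well the report tracks infection, and how common a positive stool is regardless of the report. If the report carries no information, PPV equals the background positivity and NPV equals one minus it. A broad panel read as any detection tends to push background positivity up, so PPV can look good and NPV poor with no association at all.

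The analysis list links report to pathogen within children only through PPV, the figure that carriage inflates. A high PPV could be published as evidence that self-report is accurate when non-reporters are positive just as often. The assumed 90% NPV also implies low carriage in non-reporters, which sits badly with the study's own rationale.

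**Working it through.** **Inputs from the protocol.** Stools: 20 reporting and 20 non-reporting per arm per time point (Stool sampling), so 20 × 2 × 2 = 80 in each group when pooled. Targets: 27 (Table 1). Assumed PPV and NPV: 90% each (Data analysis). Recall window: two weeks (Diarrhoea survey).

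**Assumptions.** The protocol gives no prevalence for any target. I take 0.39% to 5% per target, independent targets, and any detection counted as positive. The 80 stools per group are treated as independent.

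**1. The plan's own figure.** Half-width = 1.96 × √(p(1 − p)/n). At p = 0.90, n = 80: 1.96 × √(0.09/80) = 0.066, or ±6.6 points, which agrees with about ±7. It holds only with arms and time points pooled; at n = 40 (one arm) it is ±9.3.

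**2. What 90%/90% implies.** Positivity is 90% in reporters and 1 − 0.90 = 10% in non-reporters, an 80-point gap.

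**3. Carriage compatible with a 90% NPV.** Any-positive among k independent targets is 1 − (1 − p)^k. For 10% with k = 27: p = 1 − 0.9^(1/27) = 0.0039, or 0.39% per target. If only 14 targets mattered, p = 0.75%; if only 6, p = 1.7%.

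| Per-target prevalence in non-reporters (assumed) | Any of 27 positive | NPV | PPV if reporting is uninformative |
|---|---|---|---|
| 0.39% | 10% | 90% | 10% |
| 1% | 24% | 76% | 24% |
| 2% | 42% | 58% | 42% |
| 5% | 75% | 25% | 75% |

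**4. Table 1 against the recall window.** Child carriage can exceed 14 days for 14 of the 27 targets. For 6 of these it does so over the whole stated range, among them Giardia (about 6 months) and "Ascaris lumbricoides" (years). A child can therefore be positive long after an episode has left the recall window.

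**5. What the contrast shows.** Let c be background positivity, and a the share of otherwise negative reporters who are infected. Then PPV = 1 − (1 − c)(1 − a), NPV = 1 − c, and PPV + NPV − 1 = a(1 − c).

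- c = 0.9, a = 0: PPV 90%, NPV 10%, difference 0.
- c = 0.9, a = 0.5: PPV 95%, NPV 10%, difference 0.05.
- c = 0.1, a = 0.5: PPV 55%, NPV 90%, difference 0.45.

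The difference is zero exactly when reporting carries no information, whatever the carriage. High carriage still compresses its size, which is why a breakdown by target or group is also needed.

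**6. Precision over a range, n = 80 per group.** For PPV or NPV: ±6.6 at 90%; ±9.5 at 25% or 75%; 1.96 × √(0.25/80) = ±11.0 at 50%. For the difference, 1.96 × √(PPV(1 − PPV)/80 + NPV(1 − NPV)/80):

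- 90%/90%: 1.96 × √(0.18/80) = ±9.3
- PPV 75%, NPV 25%: 1.96 × √(0.375/80) = ±13.4
- 50%/50%: 1.96 × √(0.5/80) = ±15.5

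**The case against.** - **The any-of-27 rule is not written.** This stands. The Executive Summary also mentions biomarkers as part of the reference, and a SAP that is not shown may set a cut-off or a subset. The absence of a positivity rule is therefore not the finding, and the point is conditional on any detection counting.
- **PPV and NPV are both primary outcomes, and non-reporters are sampled in equal number.** This stands too. A reader might infer that the primary outcomes cannot show accuracy. They can: set side by side, PPV against 1 − NPV shows discrimination or its absence. What remains is that the analysis list names only PPV and plans no such contrast.
- **A low NPV is partly what the study wants to learn.** Agreed. Asymptomatic infection is an intended target, so a low NPV is not an artefact to be removed. It answers a different question from whether reporting tracks infection, and the two should be reported separately.
- **The prevalences are assumed, and targets overlap** (norovirus and human caliciviruses, for example). This stands. Positive correlation between targets gives a higher NPV than the table shows, so 76%, 58% and 25% are illustrations under independence, not upper bounds. They do not prove a 90% NPV impossible.
- **The ±7 is explicitly conditional on 90% and reproduces.** Correct. It is not an arithmetic error; the weakness is the single value on which it rests.
- **The 80 stools per group are not assured**, because Appendix 2 budgets 120 laboratory tests against the 160 stools planned. If 120 were split evenly, n = 60 per group and the half-width for the difference at 50%/50% would be 1.96 × √(0.5/60) = ±17.9 points.

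**Conclusion.** The point holds in a conditional form. If any detection counts as presence, background carriage moves PPV up and NPV down without any link between report and infection. PPV, the only predictive value in the analysis list, then cannot by itself support a conclusion about accuracy. Read together, the two primary outcomes can, but the comparison is not planned.

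The 90% NPV is unsupported and in tension with the Background and with the carriage periods in Table 1. Under independence it needs an average of 0.39% per target across 27, or 1.7% if only 6 targets matter. How far the true NPV falls short, if it does, cannot be settled from the protocol. If NPV were nearer 50%, its half-width would be ±11 points rather than about ±7.

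**What to change.** In the Data analysis section:

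1. Add NPV with its 95% CI to the analysis list, to match the primary outcomes.
2. Report PPV beside pathogen positivity in non-reporters (1 − NPV), and base the accuracy conclusion on their difference, PPV + NPV − 1, with a 95% CI. Give it overall and by target or pathogen group.
3. Keep 1 − NPV as the separate measure of asymptomatic infection, described as infection in children for whom diarrhoea was not reported.
4. Replace the single precision figure with a range for 80 pooled stools per group: about ±7 points at 90% and ±11 at 50% for PPV or NPV; for the difference, about ±9 (90%/90%), ±13 (PPV 75%, NPV 25%) and ±15.5 (50%/50%).

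This changes the analysis wording and the precision statement only. It uses the stools already planned and needs no new data. The cost is a less favourable stated precision and wide intervals for rare targets.

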The study will follow a two arm RCT design in which 400 households will be recruited through random household sampling in both the formal and informal refugee camps in Cox's Bazar (Fig.1). The random household sampling will use an EPI sampling method, in which a series of random angles and distances from a pre-determined central point (e.g. a water tap) will be generated, selecting households closest to the mapped location. This list will be generated at the beginning of the data collection period, with households randomly assigned to each research assistant.

Inclusion and exclusion criteria

Inclusion and exclusion criteria for the study is as follows:

Inclusion	Exclusion
Household has at least one child under the age of five	Household is expecting to relocate/resettle/repatriate in the next 6 months
Household has at least one adult over the age of 18	
Household consents to study	

Recruitment

Households will be initially contacted by research assistants travelling door to door who will ask to speak with an adult in the household. The study will be explained through the use of the participant information sheet, with households meeting inclusion criteria being consented and enrolled in the study. As part of consenting, GPS coordinates, name, and mobile phone number will be recorded. Households who do not consent will not have mobile phone numbers recorded, but will have GPS coordinates recorded to ensure that the house is not approached again. Mobile phone numbers and GPS coordinates will be recorded separately from data in a log book, and linked to individual household identifiers which will be recorded on the survey form.

Diarrhoea survey

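### Jaccard's index, the only measure named for the diarrhoea–marker association, has a no-association value that moves with prevalence and does not suit MUAC recorded in cm

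*Protocol*

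**What the plan says.** The Data analysis section of the protocol lists, among the analyses to be done, "The association between diarrhoea presence and other potential markers of enteric infection such as MUAC and water-related diseases", "measured for example by Jaccard's index". No other measure, reference value, confidence interval or MUAC cut-off is given in that bullet. The bullets on rate ratios and on predictive value both promise 95% confidence intervals.

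Three other places bear on the choice:

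- The Executive Summary puts the first round in February/March, "a time with low diarrhoeal disease incidence", and the second in June/July, "a time with high diarrhoeal disease incidence".
- In Appendix 3, "Mid-Upper Arm Circumference" is a single entry field in cm. It sits in the block headed "Enhanced Survey (50% of respondants"), not in the basic survey. The Diarrhoea survey section likewise describes measures of water-washed disease only under the enhanced survey.
- The only planning prevalence for diarrhoea is in the precision statement, "assuming a point prevalence of 10" per cent.

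**The concern.** Jaccard's index is the number of children with both conditions divided by the number with at least one. It describes overlap. It does not say whether the overlap exceeds what chance would give, because the chance value depends on how common each condition is. The odds ratio, by contrast, is 1 under no association at every prevalence.

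That matters here because the design varies diarrhoea prevalence between rounds on purpose. If the index is reported by round, a seasonal change in prevalence can look like a change in association. Even within one round, the index alone cannot show whether an association exists.

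The index also ignores children with neither condition. With both prevalences at 10% and no association, that is 0.9 × 0.9 = 81% of children, who are informative about association.

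Finally, the index needs two yes/no variables, while the first marker named is a measurement in cm.

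**Working it through.** **Inputs from the protocol.** "400 households will be recruited through random household sampling" (Sampling), randomised 1:1, so 400/2 = 200 per arm; diarrhoea prevalence 10% (Data analysis).

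**Assumed, because the protocol gives no figure.** Diarrhoea prevalence p of 20% or 30% in the high season; marker prevalence q between 5% and 50%.

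**The plan's own figure.** The protocol gives no figure for the index. The one figure that uses the 10% prevalence is the precision of the diarrhoea rate per arm: 1.96 × √(0.10 × 0.90 / 200) = 0.0416. This agrees with the stated ±4 percentage points, so 10% and 200 per arm are used below.

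**Value of the index with no association.** Under independence the overlap is pq and the union is p + q − pq, so

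J0 = pq / (p + q − pq).

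Its slope in p is q² / (p + q − pq)², which is always positive. With the marker prevalence held fixed, J0 therefore rises strictly with diarrhoea prevalence. Examples: 0.01/0.19 = 0.053 at 10%/10%; 0.02/0.28 = 0.071 at 10%/20%; 0.04/0.36 = 0.111 at 20%/20%; 0.09/0.51 = 0.176 at 30%/30%.

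| Marker prevalence (assumed) | Diarrhoea 10% | Diarrhoea 20% | Diarrhoea 30% |
|---|---|---|---|
| 5% | 0.034 | 0.042 | 0.045 |
| 10% | 0.053 | 0.071 | 0.081 |
| 20% | 0.071 | 0.111 | 0.136 |
| 30% | 0.081 | 0.136 | 0.176 |
| 50% | 0.091 | 0.167 | 0.231 |
| Equal to diarrhoea | 0.053 | 0.111 | 0.176 |

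**When the rise cancels.** If diarrhoea doubles from 10% to 20%, a marker at 20% must halve to 10% to hold J0 at 0.02/0.28 = 0.071.

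**Comparison with a real association.** For odds ratio 2, the overlap is a = (s − √(s² − 8pq)) / 2 with s = 1 + p + q, and J = a / (p + q − a).

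- p = q = 10%: s = 1.2, a = 0.0169, J = 0.0169/0.1831 = 0.092.
- p = 10%, q = 20%: s = 1.3, a = 0.0315, J = 0.0315/0.2685 = 0.117.

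Set against the no-association values in the table:

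- Marker at 20% in both rounds: odds ratio 2 in the low season (0.117) is close to no association at 20% diarrhoea (0.111) and below no association at 30% (0.136).
- Both prevalences rising together from 10% to 20%: odds ratio 2 in the low season (0.092) is below no association in the high season (0.111).
- Marker at 10% in both rounds: there is no reversal; 0.092 exceeds both 0.071 and 0.081.

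**Sampling spread.** In 20,000 simulated samples of 200 children with no association and the marker at 20%, the index averaged 0.071 (95% range 0.016 to 0.145) at 10% diarrhoea and 0.136 (0.069 to 0.212) at 30%. The spread is wide, so a bare index without an interval would be hard to read even within one round.

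**MUAC.** The form records cm with no category. The index could be applied only after the measurement is split at a cut-off, which the protocol does not state.

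**The case against.** The best reply is that the protocol does not commit to this statistic. It says *for example*, and a statistical analysis plan that is not shown may choose another measure or set a MUAC cut-off. That stands, and the absence of a cut-off is not held against the protocol. But Jaccard's index is still the only measure offered in that bullet, and it is a stated choice that can be improved, not a detail left open.

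Second, the next bullet plans a logistic regression of diarrhoea on demographic and health variables, which would give odds ratios. This may partly cover the same ground. It does not name MUAC or water-related diseases, so it cannot be assumed to replace the bullet.

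Third, the protocol nowhere says that the index will be compared across rounds. That is correct. The misreading is a risk created by the two-season design, not a planned analysis.

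Fourth, overlap between positive markers is a legitimate descriptive question. This is accepted, and the index can stay for that purpose.

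A reader might also infer that the index would mislead between the basic and enhanced arms. The documents do not support this: MUAC and the water-washed disease measures are placed in the enhanced survey only, so there is no between-arm comparison of these associations.

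**Conclusion.** The point holds in limited form. The no-association value of Jaccard's index depends on both prevalences, and the rounds are designed to differ in one of them. Between 10% and 30% diarrhoea that value would move by 0.028 with the marker at 10% (0.053 to 0.081), by about 0.065 with the marker at 20% (0.071 to 0.136), and by about 0.12 if both rise together (0.053 to 0.176). Only the 10% is the protocol's; the other prevalences are assumptions.

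Three stronger readings go too far:

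- That the index *will* rise between seasons. It may; a large enough fall in marker prevalence cancels the rise.
- That a true association will score below no association. This depends on the assumed prevalences and does not occur with the marker fixed at 10%.
- That MUAC cannot be used at all. It can after dichotomising, at a loss of information.

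The primary outcomes are the predictive values, which this does not touch. It is a minor point and a cheap improvement.

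**What to change.** Reword the bullet in Data analysis along these lines: *The association between reported diarrhoea and each marker will be estimated by round within the enhanced survey arm: for yes/no markers, an odds ratio with 95% confidence interval; for MUAC as a continuous variable, the age- and sex-adjusted difference in mean between children with and without reported diarrhoea, with 95% confidence interval. If rounds are pooled, standard errors will be clustered by household. Jaccard's index may be added as a description of overlap.*

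Clustering is not needed within a round, because each survey form concerns one child per household.

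The cost is one sentence and slightly more analysis work. Age and sex are already on the Appendix 3 form, and the models are standard in Stata, which the protocol already specifies. No new data and no change in sample size or conduct are needed.
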